8.6.2 Chest X-ray

Chest CT is preferred over chest X-ray, particularly when progression is an important endpoint, since CT is more sensitive than X-ray, particularly in identifying new lesions. However, lesions \geq 20 mm on chest X-ray may be considered measurable if they are clearly defined and surrounded by aerated lung.

8.6.3 *CT*, *MRI*

CT is the best currently available and reproducible method to measure lesions selected for response assessment. This guideline has defined measurability of lesions on CT scan based on the assumption that CT slice thickness is 5 mm or less. When CT scans have slice thickness greater than 5 mm, the minimum size for a measurable lesion should be twice the slice thickness. MRI is also acceptable in certain situations (e.g. for body scans). Other specialized imaging or other techniques may also be appropriate for individual cases.

8.6.4 Ultrasound

Ultrasound is not useful in assessment of lesion size and should not be used as a method of measurement. If new lesions are identified by ultrasound in the course of the study, confirmation by CT is advised.

8.6.5 *Endoscopy, Laparoscopy*

The utilization of these techniques for objective tumour evaluation is not advised. However, they can be useful to confirm complete pathological response when biopsies are obtained or to determine relapse in trials where recurrence following complete response or surgical resection is an endpoint.

8.6.6 *Tumour Markers*

Tumour markers alone cannot be used to assess objective tumour response. If markers are initially above the upper normal limit, however, they must normalize for a patient to be considered in complete response.

8.6.7 Cytology, Histology

These techniques can be used to differentiate between PR and CR in rare cases if required by protocol (for example, residual lesions in tumour types such as germ cell tumours, where known residual benign tumours can remain). When effusions are known to be a potential adverse effect of treatment (e.g. with certain taxane compounds or angiogenesis inhibitors), the cytological confirmation of the neoplastic origin of any effusion that appears or worsens during treatment when the measurable tumour has met criteria for response or stable disease is advised to differentiate between response or stable disease and progressive disease.

9.0 SERIOUS ADVERSE EVENT REPORTING

The descriptions and grading scales found in the NCI Common Terminology Criteria for Adverse Events (CTCAE) will be utilized for Adverse Event (AE) reporting (version can be found in Appendix V). All appropriate treatment areas should have access to a copy of the CTCAE. A copy of the CTCAE can be downloaded from the CTEP web site:

http://ctep.cancer.gov/protocolDevelopment/electronic applications/ctc.htm.

All serious adverse events (SAE) defined as per ICH guidelines (see below) and other adverse events must be recorded on case report forms. In addition, all "reportable" serious adverse events are subject to expedited reporting using the CCTG SAE form. The term 'reportable SAE' is used in the definitions which follow to describe those SAEs which are subject to expedited reporting to CCTG.

9.1 Definition of a Reportable Serious Adverse Event

- All serious adverse events, regardless of whether they are unexpected or related to protocol treatment, occurring during the treatment period and within 30 days after the last protocol treatment administration, must be reported in an expedited manner. Any late serious adverse event occurring after this 30-day period which is related to protocol treatment must also be reported in an expedited manner (see Section 9.2 for reporting instructions).
- A serious adverse event (SAE) is any adverse event that at any dose:
 - results in death
 - is life-threatening
 - requires inpatient hospitalization or prolongation of existing hospitalization (excluding hospital admissions for study drug administration, transfusional support, scheduled elective surgery and admissions for palliative or terminal care)
 - results in persistent or significant disability or incapacity
 - is a congenital anomaly/birth defect
- Adverse events that are suspect to be immune mediated AND that require intervention with high doses of steroids are considered to be medically important events that require intervention to prevent a fatal, life-threatening or hospitalization event. They should be reported as expedited events using the SAEs reporting system.
- In addition, if a patient shows an AST or ALT ≥3 x ULN together with total bilirubin ≥2 x ULN, refer to Appendix II for further instructions on cases of increases in liver biochemistry and evaluation of Hy's Law. These cases should be reported as SAEs if, after evaluation, they meet the criteria for a Hy's law case or if any of the individual liver test parameters fulfill any of the SAE criteria.

Medical and scientific judgement should be exercised in deciding whether expedited reporting is appropriate in other situations such as important medical events that may not be immediately lifethreatening or result in death or hospitalization but may jeopardize the patient or may require intervention to prevent one of the events listed above.

9.2 Serious Adverse Event Reporting Instructions

All reportable serious adverse events must be reported using a web-based Electronic Data Capture (EDC) system being used for this trial. For details about accessing the EDC system and completing the on-line SAE report form, please refer to the CCTG Generic Data Management Guidebook for EDC Studies posted on the IND.228 section of the CCTG website (www.ctg.queensu.ca).

Within 24 hours:	Complete preliminary Serious Adverse Event Report and submit to CCTG via EDC system.
Within 7 days:	Update Serious Adverse Event Report as much as possible and submit report to CCTG via EDC system.

EDC SAE web application interruption:

In the rare event that internet connectivity to the EDC SAE system is disrupted, please print and complete a paper copy of the SAE Report, available from the trial specific website.

FAX paper SAE Report to:

IND.228 Study Coordinator Canadian Cancer Trials Group [contact]

Please use the same timelines for submission as for direct EDC reporting.

Once internet connectivity is restored, the information that was FAXED to CCTG on the paper SAE Report must also be entered by the site into the EDC SAE web application.

Local internet interruption:

If you are unable to access the EDC SAE system, and cannot access a paper copy of the SAE Report from the trial website, please phone the IND.228 trial team [contact]) to obtain a copy of the SAE Report by FAX. Once completed, the report must be FAXED back to CCTG as indicated above. Once internet connectivity is restored, the information that was FAXED to CCTG on the paper SAE Report must also be entered by the site into the EDC SAE web application.

In cases of prolonged internet interruptions, please contact the CCTG Safety Desk for further instructions [contact]).

9.3 Other Protocol Reportable Events – Pregnancy Reporting and Exposure Reporting

9.3.1 Pregnancy Prevention

Women of childbearing potential (WOCBP) and men who are enrolled in the trial must have agreed to use contraceptive method(s) as described in Eligibility Criteria 4.1.9. Investigators may wish to additionally advise the female partners of male participants about pregnancy prevention guidelines when appropriate and compliant with local policy.

A highly effective method of contraception is defined as one that results in a low failure rate (i.e. less than 1% per year) when used consistently and correctly. Highly effective methods of contraception are described in the table below. Note that some contraception methods are not considered highly effective (e.g. male or female condom with or without spermicide; female cap, diaphragm, or sponge with or without spermicide; non-copper containing intrauterine device; progestogen-only oral hormonal contraceptive pills where inhibition of ovulation is not the primary mode of action [excluding Cerazette/desogestrel which is considered highly effective]; and triphasic combined oral contraceptive pills).

Highly Effective [*] Methods of Contraception						
Barrier/Intrauterine Methods	Hormonal Methods					
 Copper T intrauterine device Levonorgesterel-releasing intrauterine system (e.g. Mirena[®])** 	 Etonogestrel implants: e.g. Implanon or Norplan Intravaginal device: e.g. ethinylestradiol and etonogestrel Medroxyprogesterone injection: e.g. Depo-Provera Normal and low dose combined oral contraceptive pill Norelgestromin/ethinylestradiol transdermal system Cerazette (desogestrel) 					
* Highly effective (i.e. failure rate of <1% per year).						

** This is also considered a hormonal method.

9.3.2 Pregnancy Reporting

If a patient becomes pregnant during the course of the study, the investigational agent should be discontinued immediately.

Pregnancy itself - occurring in female participants, and female partners of male participants - is not regarded as an AE unless there is a suspicion that the IP under study may have interfered with the effectiveness of a contraceptive medication. The outcome of all pregnancies (spontaneous miscarriage, elective termination, ectopic pregnancy, normal birth, or congenital abnormality) should be followed up and documented even if the patient was discontinued from the study.

The investigator is required to report to CCTG any pregnancy occurring in female participants, and female partners of male participants. Pregnancies occurring up to 6 months after the last dose of study treatment must also be reported.

The investigator should report the pregnancy in a timely manner, within 24 hours of learning of the pregnancy using the CCTG Pregnancy Reporting Form available from the trial webpage.

Once informed consent has been obtained, the form should be updated to provide further pregnancy information and to reflect the outcome of the pregnancy. All follow-up reports must be submitted to CCTG in a timely manner. For pregnant partner of trial participant (and pregnant participants, if required by local policy), a copy of the signed signature page of the pregnancy follow-up consent must be submitted to CCTG.

Documents outlined above (including updates) must be sent to the CCTG safety desk [contact]/[contact]).

If the pregnancy results in death, spontaneous miscarriage; is life-threatening; requires inpatient hospitalization or prolongation of existing hospitalization; results in persistent or significant disability/incapacity; is a congenital anomaly/birth defect, then an SAE report must be additionally submitted as described above. Please note, hospitalization for labour/delivery alone does not constitute an 'inpatient hospitalization' for the purposes of pregnancy reporting.

9.4 CCTG Responsibility for Reporting Serious Adverse Events to Health Canada

The CCTG will provide expedited reports of SAEs to Health Canada (Office of Clinical Trials) for those events which meet regulatory requirements for expedited reporting, i.e. events which are BOTH serious AND unexpected, AND which are thought to be related to protocol treatment (or for which a causal relationship with protocol treatment cannot be ruled out).

9.5 CCTG Reporting Responsibility to AstraZeneca

AstraZeneca will be notified of all protocol reportable serious adverse events (as defined in Section 9.1) within one working day of receipt of report at CCTG. CCTG, as sponsor, will determine regulatory reportability in Canada. AstraZeneca will be notified of all pregnancies and outcomes of pregnancies within 30 days of receipt of the report at CCTG.

9.6 CCTG and AstraZeneca Reporting Responsibilities

AstraZeneca will report all regulatory reportable serious adverse events from non-CCTG trials (Safety Updates) with durvalumab and tremelimumab to CCTG within the timelines outlined in the contract. CCTG will review these events to determine which meet the criteria (serious, unexpected, drug related) for reporting to IND.228 investigators. AstraZeneca will report these events to Health Canada.

9.7 Reporting Safety Reports to Investigators

CCTG will notify Investigators of all Safety Reports (Serious Adverse Events (SAEs) from this trial and Safety Updates (SUs) from other clinical trials) that are reportable to regulatory authorities in Canada as reported to the CCTG. This includes all serious events that are unexpected and related (i.e. possibly, probably, or definitely) to protocol treatment. The reports will be posted to the CCTG trial IND.228 web-based safety monitoring utility.

Investigators must notify their Research Ethics Boards (REBs) of events which involve corrective action(s) to be taken as a result of the event(s) such as protocol and/or informed consent changes. The date of REB Submission for these SAEs and SUs will need to be entered into the CCTG trial IND.228 web based safety monitoring utility and documentation of REB submission must be retained in the study binder on site. The REB submission template provided by CCTG can be used to assist with tracking, submission, filing and monitoring.

The submission of events to your ethics board should be done as soon as possible (we suggest within 30 days). REB submissions greater than 90 days from the date of notification will be regarded as delinquent and a major deficiency will be assigned. These safety reports are to be filed in the trial files on site.

10.0 PROTOCOL TREATMENT DISCONTINUATION AND THERAPY AFTER STOPPING

10.1 Criteria for Discontinuing Protocol Treatment

Patients who are clinically stable but meet the criteria for iUPD should be continued on treatment until the next disease assessment at least 4 weeks later. It is recommended that the next imaging assessment be no longer than 8 weeks later in order to ensure patients remain fit for salvage therapies. Clinical stability is defined as:

- Stability or improvement in performance status.
- No clinically relevant increase in disease related symptoms such as pain or dyspnea (generally understood to mean a requirement for increased palliative intervention as below).
- No requirement for increased management of disease related symptoms including increased analgesia, radiation or other palliative care.

Patients may stop protocol treatment (durvalumab \pm tremelimumab) in the following instances:

- Intercurrent illness which would, in the judgement of the investigator, affect assessments of clinical status to a significant degree, and require discontinuation of protocol therapy.
- Unacceptable toxicity as defined in Section 7.0.
- Tumour progression or disease recurrence as defined in Section 8.0; note: investigators are encouraged to continue treatment if pseudoprogression is suspected or mixed responses are seen [Wolchok 2009].
- Request by the patient.
- Completion of therapy as outlined in Section 10.2. Efforts should be made to maintain the investigations schedule and continue follow-up, even if patients discontinue protocol treatment prematurely and/or no longer attend the participating institution.

10.2 Duration of Protocol Treatment

(see Section 8.0 for response definition)

- For complete responders, therapy will continue until progression (refer to Section 7.2).
- For partial responders, therapy will continue until progression. For stable patients, therapy will continue until progression (refer to Section 7.2).
- Patients who progress (treatment failure) will stop all treatment and go off study at the time unequivocal progression is documented clinically and/or radiographically.

10.3 Therapy After Protocol Treatment is Stopped

At the discretion of the investigator.

10.4 Follow-up Off Protocol Treatment

All patients will be seen at 4 weeks after completion of protocol therapy. Thereafter, continued follow-up is not required for patients who go off protocol treatment with iCPD, except to document ongoing toxicities (until resolved to \leq grade 2) and late toxicities (including second malignancies). For patients who go off protocol treatment with CR/iCR, PR/iPR, SD/iSD or iPD ongoing and have not already started other systemic therapy, follow-up will be required every 3 months until relapse (see Section 5 for investigations to be performed). Please note for patients who go off protocol treatment with iUPD, confirmatory scans should be performed at least 4 weeks, but no longer 8 weeks, after iUPD was documented.

Final report (Form 6) will be required for all patients while study is open. Due within 2 weeks of knowledge of death (see Appendix IV - Documentation for Study).

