5.0 PATIENT EVALUATION FLOWSHEET: PRE-TREATMENT, ON STUDY, AND AFTER TREATMENT

All patients entered on study must be evaluated according to the schedule outlined below with documentation submitted according to the schedule in Appendix IV.

Required Investigations	Pre-study (≤ 7 days prior to registration)	Day 1 each cycle, and as clinically indicated	Day 1 every 12 weeks	4 weeks after completion of protocol therapy	3 month follow-up (only required for pts without confirmed PD and ongoing toxicities ¹)
History and Physical Exam					
Including: height and weight, ECOG performance status, documentation of all measurable and non- measurable disease, clinical tumour measurements (if applicable); Vital signs ² : blood pressure, heart rate, temperature	Х	Х		Х	
Laboratory Procedures/Assessments ³					
CBC, neutrophils, lymphocytes , platelets	Х	Х		X^4	X ⁴
PTT, PT/INR (if on anticoagulants)	Х	Х		X^4	X^4
Serum creatinine, creatinine clearance (calculated), electrolytes (calcium, potassium, magnesium) bilirubin, ALP, AST, ALT, LDH, albumin, glucose, amylase ⁵ , lipase ⁵ , TSH ⁶	х	Х		X^4	X ⁴
Pregnancy Test ⁷	Х	X^8			
Radiology					
Tumour Imaging (Chest, abdomen and pelvis scan; other scans as necessary to document disease) Bone scan for osteosarcoma patients	within 28 days prior to registration or 35 if negative		X9	X^{10}	X^{10}
Other Investigations			-	-	-
Tumour markers (i.e. CA-125, etc.) ¹¹ if applicable	Х				
LVEF ¹²	(within 28 days prior to registration)	on alimically indicated			
Urinalysis (dipstick – including protein, specific gravity, glucose and blood)	Х				
Archival Tumour Tissue for assessment of TILs and PD-L1 expression (pre-screening – cohort #2 only)	X ¹³				
Correlative Studies Blood Collection	X ¹⁴		See Sect	ion 12.0 for det	ails
Adverse events	Х	Continuo	usly	X^1	

footnotes on next page ...

- Every three months thereafter to follow adverse events felt related until resolved to \leq Grade 2. Adverse Events to be evaluated using the NCI Common Terminology Criteria for Adverse Events (CTCAE v4.0) (see Appendix V).

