6.0 ENTRY/REGISTRATION PROCEDURES

6.1 Entry Procedures

All registrations will be done through the CCTG web-based, password-operated Electronic Data Capture (EDC) system. Complete details regarding obtaining a password, accessing the system and registering patients will be provided at the time of study activation and are also available in the "EDC Data Management Guidebook", posted on the IND.228 trial specific web-site. If sites experience difficulties accessing the system and/or registering/randomizing patients please contact the help desk (link in EDC) or the IND.228 Study Coordinator.

All eligible patients enrolled on the study by the participating treatment centre will be assigned a serial number which must be used on all documentation and correspondence with CCTG.

The following information will be required:

- trial code (CCTG IND.228)
- patient's initials (may be coded)
- informed consent version date, date signed by patient, name of person conducting consent discussion and date signed
- confirmation of the requirements listed in Section 4.0, including dates of essential tests and actual laboratory values

6.2 Registration

Registration will be provided electronically.

Note: The validity of results of the trial depends on the authenticity of and the follow-up of all patients entered into the trial. Under no circumstances, therefore, may an allocated patient's data be withdrawn prior to final analysis, unless the participant withdraws from the trial and requests that data collection/submission cease from the point in time of withdrawal.

All eligible patients admitted to the trial will be followed by the coordinating centre. It is the responsibility of the physician in charge to satisfy himself or herself that the patient is indeed eligible before requesting registration.

All registered patients are to be followed until death or until sites are informed by CCTG that further follow-up is no longer required. The follow-up requirements for ineligible patients are outlined in Section 5.1.

The follow-up requirements for ineligible patients who have received no protocol therapy include submission of the Baseline Report only. Data submission for ineligible participants who have received at least one dose of protocol therapy should be followed according to the protocol to allow for treatment and adverse event assessment.

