13.3 Analysis of Secondary Endpoints: Efficacy Outcomes

Following completion of the study, the following will be described:

- The median and range of the duration of stable disease, defined as the time from date of stable disease as the best response to the date when progression or death is observed, based on Kaplan-Meier method.
- The median and its 95% confidence interval for time to progression, defined as time from the date of randomization to the date of progression, based on Kaplan-Meier method.
- The median and its 95% confidence interval for progression free survival, defined as time from the date of randomization to the date of progression or death, based on Kaplan-Meier method.
- The median and its 95% confidence interval for overall survival, defined as time from the date of randomization to the date of death, based on Kaplan-Meier method.

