APPENDIX IV - DOCUMENTATION FOR STUDY

Follow-up is required for patients from the time of registration and will apply to all eligible and ineligible patients. This trial will use a web-based Electronic Data Capture (EDC) system for all data collection including SAE reporting (see Section 10.0 for details regarding SAE reporting). For details about accessing the EDC system and completing the on-line Case Report Forms, please refer to the Data Management Guidebook posted on the IND.228 area of the CCTG web-site (www.ctg.queensu.ca).

Electronic Case Report Form	To be Completed/Submitted Electronically:	Supporting Documentation to be sent using Supporting Document Upload Tool*
BASELINE REPORT	Due within 2 weeks of patient registration.	Copies of signature pages of main and pre-screening consent forms; relevant pathology & radiology reports.
TREATMENT REPORT	To be completed every 3 weeks (i.e. after each cycle). Due within 2 weeks of end of course. This report documents treatment, adverse events, investigations and response assessment for each course.	Relevant radiology reports.
CORRELATIVE STUDIES	See Section 12.	
END OF TREATMENT REPORT	To be completed when patient goes off protocol treatment. Due within 2 weeks of end of protocol treatment.	
4 WEEK POST TREATMENT REPORT	To be completed once on all patients, 4 weeks after going off protocol treatment. Due within 2 weeks after contact with patient.	Relevant radiology reports.
FOLLOW-UP REPORT	Continued in-person follow-up is not required for patients who go off protocol treatment with progressive disease , except to document ongoing toxicities (until resolved to \leq grade 2) and late toxicities (including second malignancies). For patients who go off protocol treatment with response , stable disease ongoing, or unconfirmed progression , Follow-up Report to be completed every 3 months until relapse/progression. Due within 2 weeks after contact with patient.	Relevant radiology reports.
RELAPSE/ PROGRESSION REPORT	To be completed at the time of disease relapse or progression. Due within 2 weeks after contact with patient.	Relevant radiology reports.
FOLLOW-UP FOR SURVIVAL	Follow-up for survival will continue every 3 months for 2 years (e.g. by telephone).	
DEATH REPORT**	Required for all patients while study is open. Due within 2 weeks of knowledge of death.	Autopsy report, if done.

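### Sections 5.0, 10.2 and 10.4 conflict with Section 6.2 and Appendix IV on follow-up after confirmed progression, so vital status for the descriptive OS analysis could be lost at sites that read 10.4 or 5.0 alone

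*Combined protocol and SAP*

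**What the plan says.** Three places end or omit follow-up once progression is confirmed:

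- **Section 10.4.** "All patients will be seen at 4 weeks after completion of protocol therapy". After that, "continued follow-up is not required for patients who go off protocol treatment with iCPD, except to document ongoing toxicities". Late toxicities are also excepted; survival is not.
- **Section 5.0 flowsheet.** The last column is headed "3 month follow-up (only required for pts without confirmed PD and ongoing toxicities". No row or column provides for survival contact.
- **Section 10.2.** Patients who progress stop all treatment and leave the study when unequivocal progression is documented.

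Two places continue it:

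- **Section 6.2.** "All registered patients are to be followed until death or until sites are informed by CCTG that further follow-up is no longer required".
- **Appendix IV.** "Follow-up for survival will continue every 3 months for 2 years", for example by telephone. Progression is not an exclusion, and the start of the 2 years is not given. The Follow-up Report row waives only in-person follow-up after progression.

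Section 10.4 also asks for a final report on every patient while the study is open, due within 2 weeks of knowledge of death, and refers to Appendix IV.

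Section 13.3 plans "The median and its 95% confidence interval for overall survival" by the Kaplan-Meier method. It gives no censoring rule for OS.

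**The concern.** No single survival follow-up rule can be read across these sections. Taken on its own, 10.4 or the flowsheet tells a site that nothing beyond toxicity is owed on a patient with confirmed progression after the 4-week visit. If a site acts on that, active collection of vital status stops just as the patient's risk of death has, in most settings, gone up. Kaplan-Meier estimation assumes that patients censored at a given time have the same outlook as those still followed. Censoring because of progression breaks that assumption, and the OS curve then leans on patients who have not progressed.

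The death report is only a partial safeguard. It is triggered when a site learns of a death. It requires no active contact and supplies no last-known-alive date for survivors. Deaths would enter unevenly, while time lived by survivors would not be recorded.

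What is at stake is the descriptive OS estimate. The primary response rate and the two-stage decisions do not use it.

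**Working it through.** **Passages side by side**

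| Place | After confirmed progression | End of survival follow-up |
|---|---|---|
| 10.4 | 4-week visit, then toxicities only; death report when known | not stated |
| 5.0 flowsheet | no survival contact | not stated |
| 10.2 | off study | at progression |
| 6.2 | continues for all registered patients | death or release by the coordinating group |
| Appendix IV | in-person waived; survival contact every 3 months | 2 years, start not stated |

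The last two rows can coexist if release is taken to come at 2 years. The first three cannot be squared with them unless the reader supplies the in-person limit from Appendix IV.

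**Size: illustration only.** The plan has no OS or progression figures to reproduce, so every rate here is assumed.

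Inputs per month:
- progression a = ln 2/4 = 0.1733 (median 4 months)
- death without progression b = 0.02
- death after progression c = ln 2/8 = 0.0866 (median 8 months)
- k = a + b − c = 0.1066

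Loss is taken at 1 month after progression, to stand for the 4-week visit.

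*Full follow-up.* S(t) = e^(−(a+b)t) + (a/k)[e^(−ct) − e^(−(a+b)t)].
- At 12 months: 0.0983 + 1.625 × (0.3536 − 0.0983) = 0.513.
- At 12.3 months: 0.0928 + 1.625 × (0.3445 − 0.0928) = 0.502.
- The true median is therefore 12.3 months, and 12-month OS is 51%.

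*A fraction q of progressing patients lost.* The ratio of progressed to progression-free patients at risk is r(t) = (a/k)[(1−q)(e^(kt) − 1) + q(e^(k·min(t,1)) − 1)]. Kaplan-Meier then estimates the hazard h = (b + c·r)/(1 + r), and the median solves ∫h = ln 2.

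Check at q = 1: after month 1, r = 1.625 × (1.1125 − 1) = 0.183 and h = (0.02 + 0.0866 × 0.183)/1.183 = 0.0303. Then ln 2/0.0303 = 22.9; the lower hazard in the first month moves this to 23.0.

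| Share lost | Median, formula | Median, simulation (200,000 patients) | 12-month OS, formula |
|---|---|---|---|
| 0% | 12.3 | 12.3 | 51% |
| 25% | 12.9 | 12.8 | 53% |
| 50% | 13.7 | 13.6 | 56% |
| 75% | 15.2 | 15.1 | 60% |
| 100% | 23.0 | 22.7 | 70% |

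Formula and simulation agree within simulation error.

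*Deaths reported only when learned of.* Suppose active contact stops for every progressing patient, and survivors are censored at last contact. If 25, 50, 75 or 100% of later deaths reach the site, the simulated medians are 14.7, 13.3, 12.4 and 11.9 months. Full passive reporting therefore slightly understates OS.

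*Wider range.* Assumed: median progression-free survival 2 to 6 months, median survival after progression 6 to 12 months, 10 to 20% dying without progression.
- True medians run from 7.3 to 19.4 months.
- With every progressing patient lost 4 weeks after progression and no later deaths counted, 15 to 28% of deaths are captured and the medians run from 8.8 to 44.3 months.
- One scenario moved down, from 11.3 to 10.4. There the assumed hazard of death before progression, 0.2 × ln 2/2 = 0.069, exceeds that after it, ln 2/12 = 0.058.
- With contact for 2 years from progression (an assumed start), the median equalled the true value in every scenario.

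**The case against.** The strongest reply is that post-progression survival is already provided for. Appendix IV has a dedicated survival row with no exclusion for progression, opens by applying follow-up to all eligible and ineligible patients, and limits its waiver to in-person follow-up. The flowsheet's introduction sends documentation to the Appendix IV schedule, and 10.4 cites Appendix IV for the death report. The flowsheet lists investigations, so the lack of a row for a telephone call does not cancel the call. Section 6.2 covers every registered patient. A careful site could combine these correctly: visits stop and calls continue.

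Most of this stands. A reader might infer from 10.4 and 5.0 that the plan censors OS at progression, or that sites generally would. The documents do not support that. They plan the contact, they require a death report for all patients, and even a literal reading of 10.4 keeps contact until the 4-week post-treatment visit. Nor do they say that 5.0 or 10.4 overrides Appendix IV.

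It is also fair that the share of patients lost is unknown and that OS is descriptive. For scale, take 20 patients, all deaths observed and exponential survival. A 95% interval around 12.3 months is then 12.3 × exp(±1.96/√20), or 7.9 to 19.1 months, and the 25% to 75% results lie inside it.

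This does not remove the conflict. The correct reading depends on one qualifier in a forms table that 10.4 lacks. The start of the 2 years is unstated, and 13.3 has no OS censoring rule. A wide interval does not offset a shift that runs in the same direction in most scenarios.

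**Conclusion.** The inconsistency is confirmed in current text: 5.0, 10.2 and 10.4 against 6.2 and Appendix IV. Post-progression survival data are planned, so this is a risk of uneven collection rather than a plan to censor at progression. Where a site follows 10.4 or 5.0 alone, vital status could be lost from the 4-week visit, apart from deaths that the site happens to learn of.

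Under the assumed rates, the 12.3-month median would be reported as 12.8 to 15.1 months with 25% to 75% of progressing patients lost. The 22.7-month figure is a worst case: it needs every site to disregard 6.2 and the Appendix IV survival contact, with no later deaths reported. The bias is usually upwards but not always. Its actual size cannot be known from the documents.

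The effect is confined to a descriptive analysis in 13.3. OS is not among the Section 1.2 objectives, and the response-rate analysis is untouched. The passages should be reconciled; the matter does not threaten the trial's main conclusion.

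**What to change.** Reconcile Sections 5.0, 6.2, 10.2, 10.4 and Appendix IV:

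- In 10.4 and the flowsheet, say that the waiver after confirmed progression covers in-person visits and imaging only (toxicity follow-up unchanged), and add a survival-contact entry to the flowsheet.
- In 10.2, make clear that leaving the study at progression does not end survival contact.
- In Appendix IV and 6.2, state that the survival contact already planned, telephone allowed, applies to every registered patient including those with confirmed progression. Give it one start date and one end, and use the same rule in both places.
- In 13.3, add that OS is censored at the last date known alive.

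The cost is wording in five places plus one sentence in 13.3. The calls are already scheduled in Appendix IV, so no new contact type is needed. If the trial has already run under the present text, sites could be asked for a last-known-alive date or date of death for patients with confirmed progression, and the number without one reported beside the OS estimate.
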